**Table CGBC.6.1. Criteria for Categorical Changes of Interest in Vital Signs**

Parameter	Direction	Criteria	Patient Population defined by Baseline Categories
Systolic BP (mm Hg) (sitting)	Low	$\leq 90$ and decrease $\geq 20$	All patients; $>90$ ; $\leq 90$
	High	$\geq 140$ and increase $\geq 20$	All patients; $<140$ ; $\geq 140$
	PCS High	$\geq 180$ and increase $\geq 20$	All patients; $<180$ ; $\geq 180$
	Sustained Elevation	$\geq 140$ and increase $\geq 20$ at 2 consecutive visits	All patients; $< 140$ ; $\geq 140$
Diastolic BP (mm Hg) (sitting)	Low	$\leq 50$ and decrease $\geq 10$	All patients; $>50$ ; $\leq 50$
	High	$\geq 90$ and increase $\geq 10$	All patients; $<90$ ; $\geq 90$
	PCS High	$\geq 105$ and increase $\geq 15$	All patients; $<105$ ; $\geq 105$
	Sustained Elevation	$\geq 90$ and increase $\geq 10$ at 2 consecutive visits	All patients; $< 90$ ; $\geq 90$
Systolic BP or Diastolic BP (mm Hg) (sitting)	Sustained Elevation	Meeting criteria for systolic BP for 2 consecutive visits or meeting criteria for diastolic BP for 2 consecutive visits or both	All patients
Pulse (bpm) (sitting)	Low	$<50$ and decrease $\geq 15$	All patients; $\geq 50$ ; $<50$
	High	$>100$ and increase $\geq 15$	All patients; $\leq 100$ ; $>100$
	Sustained Elevation	$>100$ and increase $\geq 15$ at 2 consecutive visits	All patients; $\leq 100$ ; $>100$
Temperature ( $^{\circ}$ F)	Low	$<96^{\circ}$ F and decrease $\geq 2^{\circ}$ F	$\geq 96^{\circ}$ F
	High	$\geq 101^{\circ}$ F and increase $\geq 2^{\circ}$ F	$<101^{\circ}$ F

Abbreviations: BP = blood pressure; PCS = potentially clinically significant.

### 6.11.7. Electrocardiograms

Not applicable.

### 6.12. Blinding

This is a single-blind study. Only the investigator, site personnel, and sponsor will know the randomized treatment after randomization. Site personnel are responsible for ensuring that patients remain blinded to treatment (that is, patients must not see the AI pens before, during, or after the drug administration). See the Manual of Operations for further details regarding blinding.

### 6.13. Subgroup Analyses

Not applicable.

### 6.14. Important Protocol Deviations

Important protocol deviations that potentially compromise data integrity or patients' rights or safety will be summarized by treatment group for the ITT population. Tables and listings of

important protocol deviations for the ITT population during all study phases will be provided by randomized treatment group.

[Appendix 1](#) lists the categories, subcategories, and study-specific terms of important protocol deviations, as well as the source and method used to identify each deviation. Per the study team's discretion, for non-programmable protocol deviations, additional categories can be added to the final non-programmable protocol deviations list as deemed necessary.

### **6.15. Annual Report Analyses**

Not applicable.

### **6.16. Clinical Trial Registry Analyses**

Additional analyses will be performed for the purpose of fulfilling the Clinical Trial Registry (CTR) requirements.

Analyses provided for the CTR requirements include the following:

- A summary of AEs will be provided as a dataset, which will be converted to an XML file. Both SAEs and 'Other' AEs are summarized: by treatment group, by MedDRA PT.
- An AE is considered 'Serious' whether or not it is a TEAE.
- An AE is considered in the 'Other' category if it is both a TEAE and is not serious. For each SAE and 'Other' AE, for each term and treatment group, the following are provided:
  - number of participants at risk of an event
  - number of participants who experienced each event, and
  - number of events experienced.
- Consistent with [www.ClinicalTrials.gov](http://www.ClinicalTrials.gov) requirements, 'Other' AEs that occur in less than 5% of patients in every treatment group may not be included if a 5% threshold is chosen (5% is the minimum threshold).
- AE reporting is consistent with other document disclosures (for example, the CSR and manuscripts).

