9.2.1. Serious Adverse Events

An SAE is any AE from this study that results in 1 of the following outcomes:

- death
- initial or prolonged inpatient hospitalization
- a life-threatening experience (i.e., immediate risk of dying)
- persistent or significant disability/incapacity
- congenital anomaly/birth defect

- important medical events that may not be immediately life-threatening or result in death or hospitalization but may jeopardize the patient or may require intervention to prevent one of the other outcomes listed in the definition. Examples of such medical events include allergic bronchospasm requiring intensive treatment in an emergency room or at home, blood dyscrasias or convulsions that do not result in inpatient hospitalization, or the development of drug dependency or drug abuse.
- when a condition related to the AI pen necessitates medical or surgical intervention to preclude either permanent impairment of a body function or permanent damage to a body structure, the serious outcome of “required intervention” will be assigned.

All AEs occurring after signing the ICF are recorded in the eCRF and assessed for serious criteria. The SAE reporting to the sponsor begins after the patient has signed the ICF and has received study treatment. However, if an SAE occurs after signing the ICF, but prior to receiving study treatment, the SAE should be reported to the sponsor as per SAE reporting requirements and timelines (see Section 9.2) if it is considered reasonably possibly related to study procedure.

Study site personnel must alert Lilly or its designee of any SAE within 24 hours of investigator awareness of the event via a sponsor-approved method. If alerts are issued via telephone, they are to be immediately followed by official notification on study-specific SAE forms. This 24-hour notification requirement refers to the initial SAE information and all follow-up SAE information.

Pregnancy (during maternal or paternal exposure to study treatment) does not meet the definition of an AE. However, to fulfill regulatory requirements any pregnancy should be reported following the SAE process to collect data on the outcome for both mother and fetus.

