10.3.4. Safety Analyses

The safety analyses will be conducted for the single-blind treatment phase.

Safety data will be summarized by treatment group.

The safety and tolerability of treatment will be assessed by summarizing adverse events:

- TEAEs
 - by Preferred Term (PT)
 - by System Organ Class (SOC)
 - by maximum severity
 - considered to be related to study treatment by investigator
- SAEs, and
- AEs leading to discontinuation.

Treatment-emergent adverse events are defined as the reported AEs that first occurred or worsened during the postbaseline phase compared with baseline phase. For each TEAE, the severity level of the event (mild, moderate, or severe) will be determined by patient or physician opinion. The Medical Dictionary for Regulatory Activities (MedDRA) Lowest Level Term will be used in the treatment-emergent computation. For each Lowest Level Term, the maximum severity at baseline will be used as the baseline severity. If the maximum severity during postbaseline is greater than the maximum baseline severity, the event is considered to be treatment emergent for the specific postbaseline period. For each patient and TEAE, the maximum severity for the MedDRA level being displayed (PT, High Level Term, or SOC) is the maximum postbaseline severity observed from all associated Lowest Level Terms mapping to that MedDRA level.

For events that are gender specific, the denominator and computation of the percentage will include only patients from the given gender.

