### **6.11.4. Serious Adverse Events and Other Notable Adverse Events**

An SAE is any AE that results in one of the following outcomes:

- death
- initial or prolonged inpatient hospitalization
- a life-threatening experience (that is, immediate risk of death)
- persistent or significant disability/incapacity
- congenital anomaly/birth defect, or
- important medical events that may not be immediately life threatening or result in death or hospitalization but may jeopardize the patient or may require intervention to prevent one of the other outcomes listed in the definition. Examples of such medical events include allergic bronchospasm requiring intensive treatment in an emergency room or at home, blood dyscrasias or convulsions that do not result in inpatient hospitalization, or the development of drug dependency or drug abuse.
- When a condition related to the autoinjector (AI) pen necessitates medical or surgical intervention to preclude either permanent impairment of a body function or permanent damage to a body structure, the serious outcome of ‘required intervention’ will be assigned.

All SAEs will be summarized by PT.

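### As written, the registry SAE summary can count a serious event from the pre-injection lead-in under galcanezumab or erenumab

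*SAP*

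**What the plan says.** SAP 6.16 sets the rules for the registry dataset. On grouping: "Both SAEs and 'Other' AEs are summarized: by treatment group, by MedDRA PT". On serious events, an adverse event is classed as serious "whether or not it is a TEAE". On the remainder: "An AE is considered in the 'Other' category if it is both a TEAE and is not serious". The section names no analysis population and no onset limit for SAEs. It also says that adverse event reporting agrees with other disclosures such as the CSR.

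SAP 6.11.4, on the SAE table, says only: "All SAEs will be summarized by PT". SAP 6.11 treats everything before the injection as baseline and everything from the injection to the end of Study Period II as postbaseline. It does not say which of these the SAE table covers. The safety population (SAP 6.6) is all patients randomised and dosed, analysed by the treatment they received.

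Protocol 10.3.4, which lists SAEs among the safety summaries, says: "The safety analyses will be conducted for the single-blind treatment phase". Protocol 9.2.1 fixes when recording starts: "All AEs occurring after signing the ICF are recorded in the eCRF and assessed for serious criteria". Before dosing, reporting of an SAE to the sponsor is limited to events possibly related to a study procedure. Recording in the eCRF is not limited in that way.

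**The concern.** Randomisation and the single injection take place at Visit 3, after the first capsule test. Events recorded before then cannot have been caused by either drug. For non-serious events the registry rule screens them out through the TEAE condition. For serious events that condition is switched off and nothing replaces it, so a lead-in SAE in a patient who goes on to be dosed falls into a drug arm.

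Two things are at stake. The public SAE count for a drug could include an event that preceded it. And if the CSR follows Protocol 10.3.4 while the registry follows SAP 6.16, one lead-in SAE would make the two disagree, although SAP 6.16 says they are consistent. The sponsor and site staff know the treatment (Protocol 7.3), so the placing of such an event should be settled in the plan and not after the event is known.

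**Working it through.** The plan gives no figure on this point to reproduce. The main check is to run kinds of event through the rules.

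**Step 1: timing.** From Protocol Table CGBC.2.1, Visit 1 is Day -8 ± 2, Visit 2 (first capsule) Day -7 ± 2, Visit 3 (randomisation and injection) Day 0, and Visit 5 Day 28 ± 3. Adverse events are collected at every visit.

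**Step 2: the rules side by side.**

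| Event | Registry (SAP 6.16) | SAE table (SAP 6.11.4) | Protocol 10.3.4 |
|---|---|---|---|
| Non-serious, lead-in only | Not counted, not a TEAE | Not applicable | Outside treatment phase |
| SAE in lead-in, patient later dosed | Counted under the drug | Not stated | Outside treatment phase |
| SAE in lead-in, patient never randomised | Has no arm | Outside safety population | Outside treatment phase |
| SAE after injection, no more severe than at baseline | Counted under the drug, though not a TEAE | Counted | Inside treatment phase |
| New SAE after injection | Counted under the drug | Counted | Inside treatment phase |

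The second row is the defect. The fourth shows why the TEAE condition cannot simply be imposed on SAEs: under SAP 6.11.3 an event is treatment-emergent only if its postbaseline severity exceeds its baseline severity, so a TEAE-only rule would lose an on-treatment SAE of unchanged severity.

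**Step 3: size of one event.** With about 30 patients per arm (Protocol 10.1), one misplaced SAE adds 1/30 = 3.3 percentage points. Fisher's exact test of 1/30 against 0/30 gives p = 1.0.

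**Step 4: share of the collection window before dosing.**
- Nominal: 8/(8 + 28) = 8/36 = 22%.
- Shortest lead-in with longest follow-up: 6/(6 + 31) = 6/37 = 16%.
- Longest lead-in with shortest follow-up: 10/(10 + 25) = 10/35 = 29%.
- If Visits 1 and 2 are combined, as the schedule allows, the low end is 5/(5 + 31) = 5/36 = 14%.

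**Step 5: expected number.** The lead-in for 60 patients is 60 × 8 = 480 patient-days, or 480/365 ≈ 1.3 person-years. The documents give no SAE rate. If it is assumed to be 2 to 5 per 100 person-years, the expected count in the whole study is 1.3 × 0.02 ≈ 0.03 to 1.3 × 0.05 ≈ 0.07, before allowing for patients whose lead-in event keeps them from being dosed.

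**The case against.** The strongest reply is that the SAP 6.16 sentence classifies events and does not choose a period, and that it protects on-treatment SAEs that fail the TEAE definition. The period, on this view, comes from Protocol 10.3.4 and the required agreement with the CSR. The protective use is real and the fix must keep it. But 6.16 lies outside SAP 6.11, names neither period nor population, and puts a TEAE condition on one class of event while lifting it from the other. A programmer following it would include the lead-in SAE.

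Other parts of the reply stand and limit the point:
- A reader might infer that the SAE table in SAP 6.11.4 is also shown to count lead-in events, or that the SAP there contradicts the protocol. It does not go that far. The sentence sets no period, and Protocol 10.3.4 can be read as supplying one. It is ambiguous.
- A reader might infer that every lead-in SAE reaches an arm because eligibility is scheduled only at Visit 1. Protocol 7.2 randomises only patients who meet all enrolment criteria, adverse events are reviewed at Visit 3, capsule retention or aspiration leads to discontinuation of study treatment (Protocol 8.1.1), and the investigator may withdraw a patient (Protocol 8.2). Some affected patients would never be dosed.
- A reader might turn the 22% into a forecast that about one in five SAEs shown under a drug would pre-date it. That needs a constant SAE rate, no drug effect and no loss of affected patients before dosing. It is an illustration towards the upper end.
- A reader might see an advantage to the sponsor's drug. Lead-in events precede 1:1 randomisation, so none is expected.

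**Conclusion.** The point holds for the registry summary. Read literally, SAP 6.16 assigns to galcanezumab or erenumab an SAE that occurred between consent and the Visit 3 injection in a patient later dosed, which does not fit the treatment-phase limit in Protocol 10.3.4. For SAP 6.11.4 the finding is ambiguity only.

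The practical size is small: most probably no such event occurs, on the assumed rates in the working. If one does, it moves an arm by about 3.3 points, assuming 30 patients per arm. The primary analysis, type I error and power are unaffected. The case for correcting it rests on a public output, an unblinded sponsor and a low cost.

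**What to change.** In SAP 6.16, and for consistency in 6.11.4:
- Name the safety population, by treatment received.
- Count under a drug only SAEs that begin, worsen or first become serious at or after the injection, whether or not they meet the TEAE definition. The words about becoming serious are needed so that an event that starts in the lead-in and turns serious after dosing, at unchanged severity, is not lost from the arm.
- Report SAEs that were serious before the injection separately as lead-in events, not assigned to a drug. State how an event that was serious before the injection and worsens after it is shown, for example under the drug with a flag.
- Reconcile both sections with Protocol 10.3.4, so that registry and CSR counts agree.

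The cost is a few sentences and one extra column or listing. The injection date and time are already recorded (SAP 6.11.1), and the TEAE derivation already needs event timing relative to the injection. The documents do not say whether the date on which an event became serious is captured, so that should be confirmed. If the registry format does not take a lead-in column, a separate listing serves the same purpose.

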## 8. Appendices

## Appendix 1. Description of Important Protocol Deviations

**Table CGBC.APP.1.1. Description of Important Protocol Deviations**

Category	Subcategory	Study-Specific	Source	Comments
Informed consent	Informed Consent Not Obtained	No re-consent for safety update	Non-programmable – Monitor identified	
		Procedure done prior to or without consent	Programmable – Statistics	Check that Visit 1 date is not before informed consent date
Eligibility	Inclusion/Exclusion	Age <18 or >55 years old at study entry	Programmable – Statistics	
		No diagnosis of migraine	Non-programmable – Monitor identified	
		On >1 other migraine preventive medication	Non-programmable – Study team identified	1) Stats will create the list of patients who meet this IPD criteria based on a list of medications from Medical. 2) Among those, the true IPDs will be manually added into a non-programmable excel sheet.
		Number of headache days $\geq 15$ per 30 day period at baseline	Non-programmable – Monitor identified	
		Female patients with positive urine pregnancy test	Non-programmable – Monitor identified	
		<3 bowel movements in the 7 days prior to Visit 1	Programmable – Statistics	
		History of IBS or chronic constipation	Programmable – Statistics	
		Hx bezoar, dysphagia, stricture, fistula, GI obst	Programmable – Statistics	
		History of GI surgery	Non-programmable – Monitor identified	
		History of abdominal surgery in past 3 months	Non-programmable – Monitor identified	
		History of bariatric surgery	Non-programmable – Monitor identified	
		History of Crohn’s, celiac, UC, or diverticulitis	Programmable – Statistics	

**Description of Important Protocol Deviations**

Category	Subcategory	Study-Specific	Source	Comments
Eligibility	Inclusion/Exclusion	Diagnosed with type 1 or type 2 diabetes	Programmable – Statistics	
		Have pacemakers or other electromechanical devices	Programmable – Statistics	
		BMI ≥ 40 kg/m 	Programmable – Statistics	
		Women who are pregnant or nursing	Non-programmable – Monitor identified	
		Drug/alcohol abuse within 1 year prior to Visit 1	Non-programmable – Monitor identified	
		Acute, serious, or unstable medical condition	Non-programmable – Monitor identified	
		History of cardiovascular events in past 6 months	Non-programmable – Monitor identified	
		Suicidal or at significant risk for suicide	Non-programmable – Monitor identified	
		Taken mAb CGRP antagonist within past 6 months	Non-programmable – Study team identified	1) Stats will create the list of patients who meet this IPD criteria based on a list of medications from Medical. 2) Among those, the true IPDs will be manually added into a non-programmable excel sheet.
		Taken oral CGRP antagonist within 14 days	Non-programmable – Study team identified	1) Stats will create the list of patients who meet this IPD criteria based on a list of medications from Medical. 2) Among those, the true IPDs will be manually added into a non-programmable excel sheet.
		Allergy to therapeutic proteins or CGRP antagonist	Non-programmable – Monitor identified	
		Allergic to SmartBar ingredients	Non-programmable – Monitor identified	
Other inadvertent enrollment	Non-programmable – Monitor identified			
Safety	SAEs	SAEs not reported in 24 hours	Non-programmable – Monitor identified	
Administrative/ Oversight	Suspected Misconduct	Suspected fraud	Non-programmable – Monitor identified	
		Privacy breach	Non-programmable – Monitor identified	

**Description of Important Protocol Deviations**

Category	Subcategory	Study-Specific	Source	Comments
Administrative/ Oversight	Other	Quality issue at site or vendor	Non-programmable – Monitor identified	
Study Procedures	Excluded Conmeds	Taking agents that affect GI motility	Non-programmable – Study team identified	1) Stats will create the list of patients who meet this IPD criteria based on a list of medications from Medical. 2) Among those, the true IPDs will be manually added into a non-programmable excel sheet.
		Taking CGRP antagonists	Non-programmable – Study team identified	1) Stats will create the list of patients who meet this IPD criteria based on a list of medications from Medical. 2) Among those, the true IPDs will be manually added into a non-programmable excel sheet.
		Taking medications that affect gastric pH	Non-programmable – Study team identified	1) Stats will create the list of patients who meet this IPD criteria based on a list of medications from Medical. 2) Among those, the true IPDs will be manually added into a non-programmable excel sheet.
	Equipment	WMC patient education	Non-programmable – Monitor identified	
		WMC calibration	Non-programmable – Monitor identified	
		WMC assessment of expulsion	Non-programmable – Monitor identified	
	Other	Study treatment administration	Non-programmable – Monitor identified	
Investigational Product	Patient took medication not fit for use	Patient received drug declared “Not Fit for Use”	Non-programmable – Monitor identified	
	Unblinding	Unjustified unblinding of patient treatment assignment	Non-programmable – Monitor identified	

Abbreviations: BMI = body mass index; CGRP = calcitonin gene-related peptide; GI = gastrointestinal; Hx = history; IBS = irritable bowel syndrome; IPD = important protocol deviation; mAb = monoclonal antibody; obst = obstruction; SAE = serious adverse event; Stats = Statistics; UC = ulcerative colitis; WMC = wireless motility capsule.

Leo Document ID = d175c1e3-062e-4757-85aa-db5774c7fac0

Approver: PPD

Approval Date & Time: 29-Sep-2020 17:14:06 GMT

Signature meaning: Approved
